## NCT03715803

## Statistical Analysis Plan

## EXPERIMENTAL DESIGN

#### **HYPOTHESIS**

The hypothesis is that the low weight Ca S mesh reduces complications while maintaining the therapeutic effectiveness of the high weight Ca A mesh.

#### STUDY ENDPOINTS

The primary outcome of this retrospective study is to evaluate the effectiveness of Calistar A or Calistar S pelvic floor repair systems. Cure is defined according to Barber criteria (1):

- Lowest point of POP-Q < 0 (no points beyond the hymen)
- No subjective bothersome symptoms (absence of vaginal bulge symptoms)
- No re-treatment/interventions on year post procedure.

The secondary outcomes of this retrospective study are the objective (anatomical) and subjective ([disease specific] quality of life) outcome of anterior and apical prolapses treated with Calistar A or Calistar S.

Other outcomes are follow-up time, blood loss during surgery, operating time, operative and postoperative complications, any recurrent prolapse according to the POP-Q classification, repeat surgery for prolapse, mesh erosion, mesh shrinkage, vaginal pain.

#### SAMPLE SIZE

For this retrospective study all patients who received a Calistar A or Calistar S implant between January 1st 2011 and April 30th 2017 and who meet all the inclusion criteria describe in *6.2.1 Inclusion criteria* will be eligible for enrolment. Patients who meet at least one of the exclusion criteria listed in *6.2.2 Exclusion criteria* will be excluded. A total of 200 subjects are planned to be included in this clinical study, distributed among research centres, gives the possibility of having results with a significance level of 0.05 (95%) with a minimum discriminant power of 80%. The multicenter aspect will guarantee a sufficient number of patients to be included in the study.

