Calistar A vs. Calistar S - Comparative Cohort Retrospective Analysis of Single Incision POP Systems

ID: CaSCaA Version number: Ver_03 Date: 28/05/2018

NCT03715803

Study Protocol

CALISTAR A VS CALISTAR S – COHORT RETROSPECTIVE ANALYSIS

(Ver_03 - 28/05/2018)

PROTOCOL APPROVAL

Responsible/Protocol Author/PI

(dd/mm/yyyy)

This protocol has been designed in accordance with the principles of Good Clinical Practices, EN-ISO 14155, Declaration of Helsinki and other applicable regulatory requirements.

SIGNATURE PAGE

CALISTAR A VS CALISTAR S – COHORT RETROSPECTIVE ANALYSIS

(Ver_03 - 28/05/2018)

I have read this protocol and agree to adhere to the requirements. I will provide copies of this protocol and all pertinent information to the study personnel under my supervision and my hospital ethics committee / institutional review board (EC/ORB). I will discuss this material with them and ensure they are fully informed regarding the device and the conduct of the study according to this protocol, applicable laws, and applicable regulatory requirements including Good Clinical Practices.

Clinical Site Name

Site Principal Investigator Signature

Date

Site Principal Investigator Printed Name

TABLE OF CONTENTS

SIGNATURE PAGE	3
Table of contents	4
GENERAL INFORMATION	5
BIBLIOGRAPHY	7

GENERAL INFORMATION

Protocol ID	
Short title	CALISTAR A VS CALISTAR S – Cohort retrospective analysis
EudraCT number	N/a
Version	3.0
Date	28/05/2018
Coordinating investigator/project leader	Dr. [name], Gynecologist
	Hospital Universitario Austral, Department of gynaecology
	[name],
	Argentina
	[name]
	[contact]
Principal investigators	See Annex 1
Sponsor	N/a
Product	Calistar A and Calistar S Single Incision POP System from
	Promedon. The products which are the object of this study have
	the approval according the CE-Guideline 93/42/EWG.
Objective	To compare the initial outcomes and complication of a high
	weight and a low weight meshes, Calistar A and Calistar S,
	respectively, implanted through a single incision to treat anterior
	and apical prolapses.
Study design	Multicentre, post-market, retrospective, two arms, non-
	randomized comparative study.
Study population	Adult female
Main study parameters/ primary	Effectiveness of Calistar S and Calistar A will be assessed by cure
endpoints	criteria of Barber, that is:
	- Lowest point of POP-Q < 0 (no points beyond the hymen)

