#### STATISTICAL ANALYSIS

Demographic and baseline characteristics will be summarized using standard descriptive methods.

The primary outcome is a compound score and will be reported as the percentage of patients that meet all 3 criteria (with the confidence interval around that percentage). Paired t-test for continuous variables and non-parametric (Wilcoxon or Mann-Whitney U) test for percentages differences between pre- and post-operative will be calculated. Sensitivity analysis will be performed for the primary endpoint.

Secondary outcomes will be presented as percentages with 95% CI for dichotomous outcomes, means with 95% confidence intervals for continuous normally distributed variables and medians

with interquartile ranges for non-normally distributed variables. Differences between baseline and post-operative follow-up for the questionnaire scores will be calculated. Comparison between Calistar A and Calistar S pelvic floor repair systems will be performed.

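### The A-versus-S comparison ignores implant date across a 6.33-year eligibility window, so if the two meshes were used at different times a period effect could be read as a mesh effect

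*SAP*

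**What the plan says.** The Protocol's study design entry describes a multicentre, retrospective, non-randomised comparison of two arms. The SAP's Hypothesis section expects that "the low weight Ca S mesh reduces complications while maintaining the therapeutic effectiveness of the high weight Ca A mesh". Its Sample Size section makes eligible "all patients who received a Calistar A or Calistar S implant between January 1st 2011 and April 30th 2017", subject to the inclusion and exclusion criteria, and adds that "A total of 200 subjects are planned to be included in this clinical study, distributed among research centres". It does not say how the 200 divide by mesh, centre or year.

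Under Statistical Analysis, baseline data are handled descriptively: "Demographic and baseline characteristics will be summarized using standard descriptive methods". The tests named there are for change from before to after surgery. The between-mesh analysis is one sentence: "Comparison between Calistar A and Calistar S pelvic floor repair systems will be performed". No model, covariate, stratum or matching rule is given, and implant date, centre and surgeon are not mentioned as analysis variables. One further sentence could bear on the matter: "Sensitivity analysis will be performed for the primary endpoint". It does not say what that analysis will contain, and it does not extend to complications.

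**The concern.** Nothing in a retrospective, non-randomised design makes the two meshes share the same calendar period, and nothing in the SAP requires that both were in use at the same time in the same centre. If centres moved from one mesh to the other during the window, the earlier mesh becomes in effect a historical control. Surgical technique, experience with single-incision mesh and completeness of records may all change over six years, and such changes would then run together with device.

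Adjusting for patient characteristics, or for centre alone, would not remove this, because a single centre can supply one mesh in its early years and the other in its late years. The plan would make the same comparison whether overlap in use was complete or absent, and a reader of the results could not tell which.

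The complication half of the hypothesis is the more exposed. If S was the later mesh and complications fell over time for other reasons, S would look safer with no mesh effect. If A was the later mesh, the bias would run the other way.

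**Working it through.** **The plan's own figure.** The SAP ties 200 subjects to a "significance level of 0.05 (95%) with a minimum discriminant power of 80" percent. This cannot be reproduced: no event rates, difference, margin, sidedness or split by mesh is stated. The calculations below therefore rest on assumptions, named as such.

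**Inputs from the documents.** Window 1 January 2011 to 30 April 2017, both ends included: 2312 days / 365.25 = 6.33 years. Total 200. Significance level 0.05.

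**Assumptions.** 100 women per mesh, no true mesh effect, complication risk centred on 15%, two-sided test.

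**Step 1: false positives from drift.** Spurious shift d = drift per year × gap in mean implant date. Set p1 = 0.15 + d/2 and p2 = 0.15 − d/2, with SE = √[(p1(1−p1) + p2(1−p2))/100]. The rejection probability is Φ(d/SE − 1.96) + Φ(−d/SE − 1.96).

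| Drift × gap | d | Risks | SE | d/SE | P(p<0.05) |
|---|---|---|---|---|---|
| none | 0 | 15% v 15% | 0.0505 | 0 | 5.0% |
| 1 point × 2 years | 2 points | 16% v 14% | 0.0505 | 0.40 | 6.8% |
| 1 point × 3 years | 3 points | 16.5% v 13.5% | 0.0505 | 0.59 | 9.1% |
| 2 points × 3 years | 6 points | 18% v 12% | 0.0503 | 1.19 | 22.2% |

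A two-era model gives a similar range. If risk falls from 20% to 10% between eras, with 75% of A but 25% of S implanted early, the spurious difference is 17.5% − 12.5% = 5 points and the false-positive rate is 16.7%. With a fall from 15% to 10% and the same imbalance the rate is 8.3%. With both meshes split evenly between eras it stays at 5%.

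**Step 2: how large a gap is possible.** If implants are spread evenly over the window and split 1:1, the largest gap in mean implant date occurs when one mesh fills the first half and the other the second: 6.33/2 = 3.16 years. A 3-year gap is 3/3.16 = 95% of that maximum, so the 22% row describes nearly sequential use. A 4-year gap would need implants clustered at the two ends of the window.

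**Step 3: what adjustment costs.** Under even spread the standard deviation of implant date is 6.33/√12 = 1.827 years. With a 1:1 split the correlation between mesh and date is r = gap/(2 × 1.827). Adjusting for linear year multiplies the variance of the mesh effect by 1/(1 − r²), and the effective total is 200 × (1 − r²).

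| Gap | r | Variance inflation | Effective total |
|---|---|---|---|
| 1 year | 0.27 | 1.1 | 185 |
| 2 years | 0.55 | 1.4 | 140 |
| 3 years | 0.82 | 3.1 | 65 |

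At the assumed 15%, 200 women yield about 0.15 × 200 = 30 complications, which supports few adjustment terms.

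**The case against.** The strongest reply is that bias needs two things together: unequal use of the meshes over the window, and outcomes that drift with time. The documents show neither. That stands. A reader might infer that the comparison is biased in favour of S, or that A was the earlier mesh. The text supports no such reading, and with even use over time there is no period bias at all. Nor is the long window itself an error; the gap is that nobody is asked to check overlap.

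A reader might also infer that drift would falsely support both halves of the hypothesis, and might calculate a false-positive rate for cure as well. That does not follow. The hypothesis is that effectiveness is maintained, so the relevant error is wrongly concluding maintenance. The rate of significant differences in cure does not measure that error, and no margin is stated from which it could be calculated. Nor does the SAP say that every implant in the window will be analysed: they are eligible, 200 are planned, and how the 200 are selected is not stated.

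The sensitivity analysis promised for the primary endpoint could in principle address implant period, but nothing says so, and complications are not covered. Implant period is also only one of several unaddressed confounders. It still needs separate mention, because adding patient or centre covariates would leave it untouched. Finally, part of the SAP and the eligibility sections it cites as 6.2.1 and 6.2.2 are not in the text supplied, so the finding covers the supplied text only.

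**Conclusion.** The point holds as a conditional one. What is certain is the omission: a non-randomised mesh comparison over 6.33 years, with no reference to implant date and no check of concurrent use. What is unknown is whether this biases the result, by how much and in which direction.

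Under the stated assumptions, the false-positive rate for complications is about 7% to 9% for spurious shifts of 2 to 3 points. It reaches about 22% for 6 points, a case close to no overlap if implants are spread evenly. The SAP should be changed on this point, mainly because the check is cheap and because without it a mesh effect and a period effect could not be told apart in the report.

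**What to change.** Amend the SAP's Statistical Analysis section as follows.

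1. Tabulate implants by device, centre and year before any outcome is compared.
2. For both cure and complications, specify a comparison restricted to, or stratified by, the centre-periods in which both meshes were implanted. For cure this can form part of the sensitivity analysis already promised.
3. Where overlap is adequate, adjust the A-versus-S comparison for implant period. Do not also require the surgeon's sequential case number; about 30 complications at the assumed rate would not support it well.
4. Where overlap is little or nil, state that mesh and period effects cannot be separated, and draw no causal conclusion about the mesh.

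Implant date is already needed to apply the eligibility window, so the table needs device, centre and a date that must be known anyway. The real cost is precision. Intervals widen in the restricted analysis, which uses fewer women, and in the period-adjusted one, by the inflation shown in step 3 of the working. At a 3-year gap adjustment leaves the information of about 65 women out of 200, which is why the overlap table should come first and the limit on the conclusion should be written in advance.

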#### STATISTICAL ANALYSIS

Demographic and baseline characteristics will be summarized using standard descriptive methods.

The primary outcome is a compound score and will be reported as the percentage of patients that meet all 3 criteria (with the confidence interval around that percentage). Paired t-test for continuous variables and non-parametric (Wilcoxon or Mann-Whitney U) test for percentages differences between pre- and post-operative will be calculated. Sensitivity analysis will be performed for the primary endpoint.

Secondary outcomes will be presented as percentages with 95% CI for dichotomous outcomes, means with 95% confidence intervals for continuous normally distributed variables and medians

with interquartile ranges for non-normally distributed variables. Differences between baseline and post-operative follow-up for the questionnaire scores will be calculated. Comparison between Calistar A and Calistar S pelvic floor repair systems will be performed.

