	- No subjective bothersome symptoms (absence of vaginal bulge
	symptoms)
	- No re-treatment/interventions on year post procedure.

Secondary endpoints	The secondary endpoint is defined as the objective assessment of
	POP by POP-Q. POP-Q staging will be compared pre- and post-
	operative.
	The subjective outcome is defined as the assessment of
	subjective symptoms resulting from POP by validated quality of
	life (QoL) questionnaires (improvement of the QoL of the subjects
	compared to the baseline values):
	- Pelvic Floor Distress Inventory (PFDI 20) to assess the impact of
	urinary, prolapse and colorectal distress post-operative.
	- Pelvic Organ Prolapse/ Urinary Incontinence Sexual
	Questionnaire (PISQ-12) to evaluate sexual function in women
	with pelvic organ prolapse and/or urinary incontinence post-
	operative.
	- Patient Global Impression to evaluate patient satisfaction with
	the experience and the result of procedure.
	Type of surgery and operative time will be compared for both
	pelvic floor systems repair.
Safety endpoints	Operative complications such as bladder injury and blood loss will
	be evaluated. Complications related to the use of meshes such as
	vaginal pain, infection and mesh erosion will be assessed.
Inclusion criteria	Female;
	Anterior and apical prolapse Stage 3 (according to POP-Q) or
	more with or without SUI;
	Primary or recurrent treatment with Calistar S or Calistar A;
	At least 6 months follow-up
Exclusion criteria	Recurrent vaginal infections;
	Chronic colorectal diseases (chronic nonspecific ulcerative colitis,
	diverticulitis, diverticulosis, Chron's disease, irritable bowel
	syndrome, familial polyposis);
	Presence of any coagulopathies;
	Impairment of the immune system or any condition that
	compromises recovery;
	Prior irradiation;
	Chronic pelvic pain

BIBLIOGRAPHY

- 1. SCENIHR. Opinion on The safety of surgical meshes used in urogynecological surgery. 2015. 105 p.
- Amid PK. Classification of biomaterials and their related complications in abdominal wall hernia surgery. Hernia [Internet]. 1997;1(1):15–21. Available from: http://link.springer.com/10.1007/BF02426382

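### The pre/post sentence allows an unpaired test on paired data (minor), and the non-randomised Calistar S versus A comparison has no stated adjustment for case mix (weightier)

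*SAP*

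**What the plan says.** The SAP's STATISTICAL ANALYSIS section gives continuous variables a paired t-test and then, in the same sentence, says that a "non-parametric (Wilcoxon or Mann-Whitney U) test for percentages differences between pre- and post-operative will be calculated". It does not say which Wilcoxon test is meant. On questionnaires it adds: "Differences between baseline and post-operative follow-up for the questionnaire scores will be calculated".

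On the two meshes, the protocol's Objective opens "To compare the initial outcomes and complication of a high" and goes on to name the heavier and the lighter mesh. The SAP's HYPOTHESIS section states: "The hypothesis is that the low weight Ca S mesh reduces complications while maintaining the therapeutic effectiveness of the high weight Ca A mesh". The protocol describes a multicentre, retrospective, two-arm study without randomisation. Its inclusion criteria admit "Primary or recurrent treatment with Calistar S or Calistar A" and prolapse of Stage 3 or above. SAMPLE SIZE takes implants from January 2011 to April 2017, with 200 women "distributed among research centres".

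The analysis of that contrast is given in one sentence: "Comparison between Calistar A and Calistar S pelvic floor repair systems will be performed". Baseline data appear only here: "Demographic and baseline characteristics will be summarized using standard descriptive methods". A sensitivity analysis of the primary endpoint is promised, but its content is not given. The available text names no between-mesh estimate, model, covariate, matching, weighting or stratification.

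**The concern.** **Paired data, unpaired test.** Mann-Whitney U treats the before and after values as two separate groups of women. When the two values are positively correlated, it uses too large a standard error. Real but modest changes in yes/no outcomes can then be missed.

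**Unadjusted comparison of meshes.** Without randomisation, the women given S and the women given A may differ in prognosis. Primary versus recurrent prolapse is one visible route; baseline stage, age, centre and implant date are others. A crude difference in cure mixes the effect of the mesh with that of case mix, and the bias can go either way. It could make S seem to hold its effectiveness when it does not, or the reverse. If the covariates are not fixed beforehand, an adjusted analysis added later is open to choice after seeing the results.

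**Working it through.** The documents give N = 200 and a significance level of 0.05. They give no split by mesh, cure rates, correlations or case mix, so **every other input below is an assumption**. The plan states no figure on this point to reproduce.

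**1. Paired yes/no outcome: 100 pairs, 50% before and 35% after, correlation phi**

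- Probability of yes at both times: p11 = 0.50 × 0.35 + phi × √(0.50 × 0.50 × 0.35 × 0.65).
- Discordant shares: b = 0.50 − p11 and c = 0.35 − p11. The difference is 0.15.
- True SE = √[(b + c − 0.15²)/100].
- McNemar's null SE = √[(b + c)/100].
- Mann-Whitney's SE ignores pairing: √(2 × 0.425 × 0.575/100) = 0.0699.
- Power ≈ Φ[(0.15 − 1.96 × SE used)/true SE].

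| phi | b, c | true SE | McNemar SE | Power, Mann-Whitney | Power, McNemar |
|---|---|---|---|---|---|
| 0 | 0.325, 0.175 | 0.0691 | 0.0707 | 57% | 57% |
| 0.3 | 0.2535, 0.1035 | 0.0578 | 0.0597 | 59% | 72% |
| 0.5 | 0.2058, 0.0558 | 0.0489 | 0.0511 | 60% | 85% |

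Simulation gives about 60% and 62% for Mann-Whitney against 73% and 87% for McNemar at phi 0.3 and 0.5.

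With no true change (50% at both times), Mann-Whitney's type I error is about 2Φ[−1.96/√(1 − phi)]. That is 1.9% at phi 0.3 and 0.6% at phi 0.5 (simulated 2.2% and 0.8%), so the test errs on the conservative side.

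For large changes the loss disappears. In simulation at phi 0.3, a fall from 90% to 70% has power 98.0% against 99.3%, and a fall from 60% to 30% has 99.9% against 100%.

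**2. Crude comparison of meshes: 100 women per mesh, no true mesh effect**

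- Bias (S minus A) = (recurrent share in S − share in A) × (recurrent cure − primary cure).
- Main case, with cure 90% primary and 70% recurrent, and recurrent share 20% in A and 40% in S: (0.40 − 0.20) × (0.70 − 0.90) = −0.04.
- Expected crude cure: A = 0.8 × 0.90 + 0.2 × 0.70 = 86%; S = 0.6 × 0.90 + 0.4 × 0.70 = 82%.
- SE = √(0.86 × 0.14/100 + 0.82 × 0.18/100) = 0.0518, so |bias|/SE = 0.773.
- Coverage of the 95% CI ≈ Φ(1.96 − 0.773) − Φ(−1.96 − 0.773) = 88%.

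| Recurrent cure | Share A, share S | Bias | Coverage |
|---|---|---|---|
| 80% | 20%, 40% | −2 points | 93% |
| 70% | 20%, 40% | −4 points | 88% |
| 70% | 50%, 20% | +6 points | 79–80% |

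Reversing the shares reverses the sign. With 40% recurrent in A and 20% in S, the bias is +4, so a true deficit of 10 points for S would appear as about −6.

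**3. What adjustment does and costs (simulated)**

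In these cases, a risk difference standardised from a logistic model that includes primary/recurrent status has bias of at most 0.2 points and coverage of 94–95%. This is favourable by construction, because the only confounder is measured and modelled. CI width goes from 20.1 to 20.2 points in the 4-point case and from 20.6 to 21.4 in the 6-point case.

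Centre is different. With four assumed centres added, mean width stays near 20 points if both meshes are used evenly. It rises to about 25, 34 and 47 points if mesh use splits 80/20, 90/10 and 95/5 between centres.

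**The case against.** **On the paired test.** The valid option may be intended. The sentence opens with a paired t-test, joins Wilcoxon and Mann-Whitney U with an or, and may have meant the latter for S versus A. This stands as a reason to rate the point minor. A reader might infer that the SAP requires an invalid test, inflates false positives, or leaves questionnaire scores without a paired analysis. The text supports none of these: the test is optional, its error is conservative, and scores treated as continuous get a paired t-test. Women enter at Stage 3 or above, so large anatomical changes are plausible, and there the choice hardly matters. The defect also leaves the S-versus-A objective untouched.

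**On adjustment.** The promised sensitivity analysis could contain an adjusted model, and the SAP cites sections that are not in the available text. Both are fair limits. But the cited sections are referenced for eligibility, and an undefined sensitivity analysis fixes no covariates. A reader might also infer that the S-versus-A result is known to be confounded. The documents do not show that case mix differed by mesh; the 4-point figure only illustrates what would follow if it did.

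**On the remedy.** Adjustment is not free of cost or certain to succeed. The centre results above bear this out, and unmeasured confounding would remain.

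**Conclusion.** Both parts hold for the text available, with different weight.

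1. **Wrong as written, minor.** Mann-Whitney U is offered for paired pre/post percentages. At modest changes and phi 0.3 to 0.5, it loses roughly 13 to 25 points of power against McNemar (73 − 60 and 87 − 62). At zero correlation or for large changes it loses almost nothing.
2. **A worthwhile improvement, and the weightier part.** The central comparison is non-randomised and has no stated adjustment. Under the assumed case-mix differences, crude bias is 2 to 6 points and coverage falls to between 93% and about 80%; the main case gives 4 points and 88%. Without a case-mix difference there is no such bias. The documents do not say which situation applies, which is a reason to settle the adjustment before seeing outcomes.

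**What to change.** **Pre/post sentence.** Delete Mann-Whitney U. Name McNemar for paired yes/no outcomes and the Wilcoxon signed-rank test for paired ordinal or non-normal outcomes. Keep Mann-Whitney U for comparisons between the meshes. This costs one sentence.

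**Comparison of meshes.** Add a short paragraph to STATISTICAL ANALYSIS:

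- Report the crude cure risk difference, S minus A, with its 95% CI.
- Beside it, report a risk difference standardised from a logistic model with covariates fixed in advance: primary or recurrent prolapse, baseline POP-Q stage and age.
- Add centre, and consider implant period and follow-up length, only where both meshes are adequately represented, for example as the content of the sensitivity analysis already promised.

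**Costs and limits.** The list must stay short: at an assumed 85% cure, 200 women give 200 × 0.15 = 30 failures. Widening is small for the patient-level covariates but can be large for centre. Where a centre used only one mesh, its own data cannot separate centre from mesh. The SAP does not list the baseline characteristics it will summarise, so the availability of these covariates in the records must be confirmed first. Adjustment does not remove unmeasured confounding, and the report should say so.

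### The study's question is Calistar S against Calistar A, but the SAP gives that contrast no effect measure, no adjustment for confounding and no criterion for maintained effectiveness

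*SAP*

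**What the plan says.** The SAP's Hypothesis section states a contrast between devices: "the low weight Ca S mesh reduces complications while maintaining the therapeutic effectiveness of the high weight Ca A mesh". The Protocol's Objective agrees; it opens "To compare the initial outcomes and complication of a high" weight mesh and goes on to name the low-weight one. The Protocol describes the design as comparative and non-randomised.

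The SAP's Statistical Analysis section then provides the following.

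- **Cure:** the "percentage of patients that meet all 3 criteria (with the confidence interval around that percentage").
- **Tests:** "Paired t-test for continuous variables and non-parametric (Wilcoxon or Mann-Whitney U) test for percentages differences between pre- and post-operative will be calculated". These are worded for change within patients, not for one device against the other.
- **Device contrast:** one sentence closing the paragraph on secondary outcomes, "Comparison between Calistar A and Calistar S pelvic floor repair systems will be performed".
- **Robustness:** "Sensitivity analysis will be performed for the primary endpoint", with no content given.
- **Baseline data:** descriptive summaries only.

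Complications are listed among other outcomes in the SAP's Study Endpoints section and under Safety endpoints in the Protocol. The Statistical Analysis section has no analysis specific to them.

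The cohort is all eligible patients who "received a Calistar A or Calistar S implant between January 1st 2011 and April 30th 2017" (SAP, Sample Size). The Protocol's Inclusion criteria admit primary and recurrent cases and ask for at least 6 months of follow-up. One of the three cure criteria is "No re-treatment/interventions on year post procedure". The POP-Q and bulge criteria carry no time point.

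**The concern.** The hypothesis has two halves: fewer complications with S, and effectiveness no worse than with A. Neither half has a defined analysis. Percentages with separate intervals do not give a difference with an interval, and the named tests address pre/post change.

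Device was not assigned at random. Primary or recurrent status, disease stage and date of implant could each differ between devices and also affect cure. If no adjustment is fixed in advance, the form of the contrast and its covariates could be chosen once the outcomes are known, and an unadjusted difference could reflect case mix.

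Some patients may have between 6 and 12 months of follow-up, and no rule says how the re-treatment criterion applies to them. If such patients are commoner in one arm, that arm has less time in which to record a failure.

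Finally, no margin or other criterion defines maintained effectiveness. Nothing in the plan prevents a non-significant difference from being read that way.

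**Working it through.** **1. The plan's own figure.** The SAP's Sample Size section gives 200 subjects, significance level 0.05 and at least 80% power. It gives no rate, effect, margin, device split, sidedness or endpoint, so the figure cannot be reproduced and does not show which contrast was intended. Several different targets give a total close to 200 (1:1 split, 80% power, two-sided 0.05 or one-sided 0.025):

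| Possible target | Total N |
|---|---|
| Cure 90% v 75% | 200 |
| Complications 15% v 3.5% | 198 |
| Standardised mean difference 0.40 | 198 |
| Non-inferiority at 90% cure, 12-point margin | 198 |

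All rates and splits from here on are assumptions. The precision and power figures are unadjusted.

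**2. Confounding.** Shift in the crude difference = (cure gap between primary and recurrent cases) × (difference between devices in the share of recurrent cases).
- 0.10 × 0.20 = 0.02, or 2 points.
- 0.20 × 0.40 = 0.08, or 8 points.

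**3. Precision and margin power.** Half-width = 1.96 × √[p(1−p)(1/nA + 1/nS)]. Power for an illustrative 10-point margin with equal true cure = Φ(0.10/SE − 1.96).

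| Cure p | Half-width, 100/100 | Power, 100/100 | Half-width, 140/60 | Power, 140/60 |
|---|---|---|---|---|
| 90% | 8.3 points | 65% | 9.1 points | 58% |
| 85% | 9.9 points | 51% | 10.8 points | 44% |
| 80% | 11.1 points | 42% | 12.1 points | 37% |

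The larger confounding shift in step 2 is close to the half-width at 90% cure.

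**4. Non-significance after a real loss.** For a true 10-point fall in cure, a two-sided 5% pooled z test at 100 per arm is non-significant 49% (90% to 80%), 58% (85% to 75%) and 63% (80% to 70%) of the time by normal approximation. Exact enumeration gives 48%, 57% and 63%.

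**5. Complications.** By exact enumeration of the pooled z test at 100 per arm, two-sided 5%, a halving of risk is significant 52% (20% to 10%), 27% (10% to 5%) and 15% (6% to 3%) of the time.

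**6. Follow-up window.** Suppose one-year cure is 80% to 90%, failures arise at a constant rate, patients seen only to 6 months without failure count as cured, and one arm has 40 points more of them.
- √0.90 = 0.949; 0.40 × (0.949 − 0.900) = 1.9 points.
- √0.80 = 0.894; 0.40 × (0.894 − 0.800) = 3.8 points.

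This applies the year to every kind of failure. If only re-treatment is tied to the year, the shift is smaller.

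**7. Minor: Mann-Whitney U on paired percentages.** Exact enumeration with 100 pairs and a bivariate-normal latent correlation; asymptotic McNemar, which equals signed-rank on binary pairs, against tie-corrected Mann-Whitney.

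| Latent correlation | Power 30% to 20%, McNemar | Same, Mann-Whitney | Type I error at 30%/30%, Mann-Whitney |
|---|---|---|---|
| 0.3 | 44% | 36% | 3.0% |
| 0.5 | 51% | 34% | 1.7% |
| 0.8 | 69% | 31% | 0.3% |

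For a change from 50% to 20%, both tests exceed 99% power.

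**The case against.** *A comparison is planned.* This is correct. A reader might infer that the SAP contains no analysis between devices, or that only type of surgery and operative time are to be compared, because the Protocol's Secondary endpoints single those two out. The documents support neither reading: the SAP promises the comparison, and the Protocol's Objective names outcomes and complications for it. What is missing is the method.

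*Cure is not defined as a one-year endpoint.* This stands. It is tempting to read all three criteria at one year, but only re-treatment refers to a year, and the Objective speaks of initial outcomes. The narrower mismatch between that year and the 6-month inclusion minimum remains.

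*The plan nowhere says that non-significance will be taken as maintained effectiveness.* Also true. Step 4 shows what an absent criterion permits, not what the plan prescribes.

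*The text may be incomplete.* The SAP cites inclusion and exclusion sections (6.2.1 and 6.2.2) that are not in the supplied text, and one portion ahead of its Hypothesis section was not available. The Statistical Analysis section itself reads as complete. This limits certainty about the rest of the document but does not fill the gap.

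*Adjustment has limits.* With 200 patients and 80% to 90% cure there would be 200 × 0.10 = 20 to 200 × 0.20 = 40 failures. The number of centres and the device split are unknown, so a long covariate list is not supportable.

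*The test wording can be read charitably.* Wilcoxon, taken as signed-rank, is valid for paired data. Mann-Whitney U on paired data with positive correlation is conservative, so it does not produce spurious findings.

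**Conclusion.** The concern holds and should be fixed before outcome data are analysed. In the supplied text, the central comparison has no effect measure, no adjustment despite non-random allocation, mixed primary and recurrent cases and implants over more than six years, and no criterion for the claim that effectiveness is maintained. This goes beyond brevity: carried out as written, the device contrast is open to confounding.

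Under the stated assumptions, case mix could shift the cure difference by 2 to 8 points and unequal follow-up by up to 1.9 to 3.8 points, against an unadjusted half-width of 8.3 to 11.1 points at 100 per arm. The documents give no rates, imbalance or split, so they do not show that the contrast will be biased or in which direction. The absence of a specified contrast and criterion rests on the text alone and does not depend on these figures.

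The mismatch between the re-treatment year and the 6-month minimum is a real secondary fault. The Mann-Whitney wording is minor.

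**What to change.** Amend the SAP's Statistical Analysis section as follows.

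(a) **Effectiveness.** Report the difference in proportion cured, S minus A, with a two-sided 95% CI. Adjust by propensity weighting or regression standardisation for a short set of recorded baseline factors: POP-Q stage, primary or recurrent case, and implant date where the devices overlap in time. Add SUI and centre only if event and device counts allow. Give the unadjusted difference as a sensitivity analysis.

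(b) **Follow-up.** Reconcile the one-year re-treatment criterion with the 6-month inclusion minimum, and state the time point for the POP-Q and bulge criteria. Count an observed failure as not cured in every analysis. In a further sensitivity analysis, take only the patients with no observed failure and unknown one-year status, and count them all as cured, then all as not cured.

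(c) **Maintained effectiveness.** Claim it only if the lower confidence limit lies above a clinically justified (negative) margin for S minus A, fixed before outcome data are analysed. Otherwise report the adjusted estimate and do not treat non-significance as support.

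(d) **Complications.** Report an adjusted risk difference between devices with 95% CI over a stated window that allows for unequal follow-up. A single key complication or a 6-month window is optional; a window that short would leave later mesh erosion out.

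(e) **Pre/post change.** Use McNemar for paired percentages and Wilcoxon signed-rank for paired ordinal or skewed data. Keep Mann-Whitney U for comparing the devices.

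**Cost.** This is SAP wording, plus a clinical justification if a margin is used. Stage, primary or recurrent status and implant date all appear in the eligibility text, so they should be on record. The last eligible implant (30 April 2017) is 393 days before the Protocol's version date (28 May 2018), so one-year status is possible by calendar for every patient, though not all may have been seen. Maintained effectiveness becomes harder to claim, as the power column in step 3 of the working shows. Adjustment may widen the interval, and the assumed 20 to 40 failures keep the covariate set small.
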